#### **2) Progression of left atrial fibrosis**

Monitoring will start at the baseline CMR scan prior to ablation and up to the end of the clinical trial.

Defined as:

- a) The percentage (%) of new fibrosis seen on the 12-month CMR scan compared to CMR scans taken at baseline and at 3-months post-ablation.

The primary endpoints will be compared between the treatment (dronedarone) and control arms (placebo) respectively.

### *Secondary Endpoints*

#### **1) AAD initiation change or adjustment**

Any initiation or adjustment to AAD therapy after ablation in either the drug or control group. Any switches or titrations after PEP of AF recurrence is reached will be included. Treating physicians will be advised to limit initiation or adjustments to AADs to essential cases (e.g. severely symptomatic study participants).

#### **2) Incidence of symptomatic AA episodes**

AA episodes associated with palpitations, chest pain, dyspnea, dizziness, syncope, or unusual fatigue and weakness. AA incidence will be assessed via the AFSS questionnaire results.

#### **3) Repeat ablation**

#### **4) Cardioversion**

#### **5) AF burden**

Defined as the percentage of time in AF during the monitoring period, 24-48 hours and, at 3-month and 12-month post-ablation (via ECG readings). It will be calculated per follow-up period for each study participant as a time-weighted average (%).

#### **6) Quality of Life (QoL)**

Evaluated by the AFEQT and AFSS questionnaires at baseline, 3-month, and 12-month follow-up visits.

#### **7) Study Participant Safety**

Study participants will be evaluated at multiple timepoints across the study: their in-person 3-month and 12-month visits and their 6, 9 and 13-month phone calls. This evaluation includes any adverse events, especially adverse events (AEs) related to AAD treatment. AEs related to dronedarone are defined in the **Safety/Adverse Event Monitoring Plan** section of this protocol.

#### **8) Pre- and Post-Ablation Left Atrial Function Changes**

LA function will be measured as the LA emptying fraction and strain using cine-MRI sequences included in the CMR imaging (Please see **Appendix B: CMR Protocol**).

#### **9) Left Ventricle (LV) Structural and Functional Changes**

LV structure, or fibrosis (%), will be assessed using native T1 and ECV MRI sequences included in the CMR imaging. LV function will be measured as the ejection fraction (LVEF) and LV strain using cine-MRI sequences performed as part of the CMR protocol (see appendix)

Secondary endpoints will be analyzed at 3 (0-3) and 13-months (0-13) post-ablation and compared between the two trial arms.

#### *Exploratory Endpoints:*

- 1) CV hospitalization**
- 2) CV mortality**
- 3) Stroke/Transient Ischemic Attacks**

---

## **Study Population**

---

Multicenter US Clinical Trial

**Total Patient Population:** 330 study participants

---

## **Inclusion Criteria**

---

Patients must meet the following criteria to be enrolled in the trial:

1. Male or female patients aged  $\geq$  18 years.
2. Patients diagnosed with paroxysmal or persistent AF (evidenced by ECG rhythm strip evaluations or written documentation) and who are undergoing ablation of atrial fibrillation, regardless of whether they were receiving an AAD before enrollment or not.

---

## **Exclusion Criteria**

---

Patients will be excluded from enrollment if any of the following criteria are present:

1. Any health-related gadolinium/MRI contraindications (e.g. allergy to gadolinium or similar agent, pacemakers, Implantable Cardioverter Defibrillators (ICD's), other devices/implants contraindicated for use of MRI, etc.)
2. Patients who are medically ineligible to be or are unwilling to be cardioverted electrically or by medications before ablation.

---

 “Paroxysmal” atrial fibrillation (AF) is defined here as an AF episode lasting within 7 days of onset and spontaneously resolving without the need for a pharmacological or electrical cardioversion. “Persistent” atrial fibrillation is defined here as any AF episode lasting beyond 7 days or any episode 7 days or less requiring a pharmacological or electrical cardioversion to terminate the abnormal rhythm.

3. Patients who have a known terminal illness with a prognosis less than 12 months at the time of the informed consent process.
4. Patients who are unable to or are unwilling to receive cardiac MRI (CMR) scans.
5. Patients who are incarcerated or become incarcerated during the trial period.
6. Patients who are unable or are unwilling to return to the study site/clinic for follow-up procedures such as, collecting IP/Placebo, collecting devices, blood draws
7. Patients who have not successfully recovered from cardiac ablation.
8. Patients who do not meet quality standards for the baseline CMR scan
9. 8. Patients weighing >300 lbs. as CMR quality may decrease with patients with increased BMI. Patients that have contraindications to dronedarone. (This includes patients with decompensated heart failure or New York Heart Association (NYHA) Class IV, second or third-degree atrioventricular (AV) block or sick-sinus syndrome [except when used in conjunction with a functioning pacemaker]), concomitant use of strong CYP-3A inhibitors or other Class I or III AADs, drugs or herbal products that prolongs the QT interval and may induce Torsade de Pointes.
10. Liver or lung toxicity related to previous use of amiodarone, severe hepatic impairment including any stage of cirrhosis, acute liver failure, and/or interstitial lung disease including pulmonary fibrosis and pneumonitis.
11. Symptomatic bradycardia <50bpm, QTc Bazett interval  $\geq$ 500ms or PR interval >280ms,
12. Hypersensitivity to the active substance of Multaq® (dronedarone) or to any of its excipients.
13. Acute or chronic severe renal disease with a low glomerular filtration rate (GFR), <30 mL per minute per 1.73 m^2 will be excluded from the trial.
14. Patients with a history of prior left atrial ablation or valvular cardiac surgery (myocardial scarring/fibrosis from prior surgeries may confound data).
15. Patients with cognitive impairments who are unable to give informed consent.
16. Patients with physical ailments which may prohibit them from actively participating in the trial.

---

 Patients may be excluded from the trial after the completion of their cardiac ablation. If it has been determined that the patient cannot tolerate the procedure well, then they should not be enrolled in the study. This determination will be made at the discretion of the patient's physician (i.e. site investigator).

 Patients who do not meet the standard baseline images should not be enrolled in the study (the decision will be made at the discretion of the imaging specialist).

## **FOR FEMALE PATIENTS ONLY:**

1. Pre-menopausal (last menstruation  $\leq$  1 year prior to screening visit) who:
  - a. Are pregnant or breast-feeding or plan to become pregnant during the study period or,
  - b. Are not surgically sterile or,
  - c. Are of childbearing potential and are unwilling to practice two acceptable methods of birth control or,
  - d. Do not plan to continue practicing two acceptable methods of birth control throughout the trial (highly effective methods of birth control are defined as those, used alone or in combination, that result in a low failure rate i.e. less than 1% per year when used consistently and correctly).

### *Study Participant Replacement*

Study participants who discontinue participation prior to the end of clinical trial will not be replaced.

### *Equal Opportunity Participation*

The EDORA trial does not and shall not discriminate on the basis of race, color, religion (creed), gender, gender expression, age, national origin (ancestry), disability, marital status, sexual orientation, or military status, in the operations of its clinical trial.

## **Treatment Groups**

---

Each patient will be randomized after their AF ablation procedure visit to receive either dronedarone or placebo (sugar pill) at discharge post-ablation. Patients partaking in this clinical trial may be newly diagnosed with AF or have undergone previous treatments for AF such as rate control, rhythm control, or direct current cardioversions.

### *Treatment Group (dronedarone [Multaq®])*

Patients randomized to receive dronedarone will receive an initial dose after their cardiac ablation procedure. If a new AAD is initiated, i.e. not dronedarone, the trial drug will be discontinued. If drug discontinuation occurs, the patient will continue to be monitored for fibrosis progression and AA recurrence/AF burden post-ablation. The evaluation of co-primary endpoints as well as all secondary endpoints will continue to be recorded throughout the duration of the trial.

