Physicians will be advised to avoid adjustments in drug therapy unless absolutely necessary (severely symptomatic patients, patients with newly diagnosed heart failure, New York Heart Association (NYHA) Class IV, etc.). Severely symptomatic patients will be defined as, study participants with non-tolerated palpitations or chest pain, dizziness, syncope, dyspnea, severe fatigue, or suddenly reduced ability to exercise.

Any initiation or change of an antiarrhythmic treatment in the treatment or control group will be considered as a secondary endpoint of the trial. Patients will continue to be monitored for fibrosis progression and AF burden via CMR scans and ECG monitoring device until the end of the follow-up period. In the case of AA recurrence after ablation, AAD initiation or change will be left to the discretion of the treating physician.

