In the case where continuous heart monitoring may have been conducted as part of standard of care), clinical staff will upload the summary report onto DACIMA.

Patients will be informed that ECG rhythm strips and associated results are not read in real-time. If any readings are positive for AF or patients experience any AF related symptoms, they are advised to seek immediate medical attention.

Preventice has a stoplight notification protocol that allows them to identify critical and serious rhythm patterns. In this case, if such a rhythm is detected, Preventice may call sites to alert them that a participant should be immediately contacted.

Each site will create a master list that associates a participant with their device for emergency circumstances. It will be the sites responsibility to contact the participant and advise them to seek medical attention, if necessary.

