## **5.2 Cardiovascular Death and Heart Failure in Permanent AF**

MULTAQ doubles the risk of cardiovascular death (largely arrhythmic) and heart failure events in patients with permanent AF. Patients treated with dronedarone should undergo monitoring of cardiac rhythm no less often than every 3 months. Cardiovert patients who are in atrial fibrillation (if clinically indicated) or discontinue MULTAQ. MULTAQ offers no benefit in subjects in permanent AF.

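### The protocol body has no trial-product provision for AF that persists without a new AAD, although Appendix C has one, and the visit windows allow 120 on-treatment days without a scheduled recording against Appendix C's 3 months

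*Combined protocol and SAP*

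**What the plan says.** **Stopping trial product.** The Treatment Group section states: "If a new AAD is initiated, i.e. not dronedarone, the trial drug will be discontinued". The Control Group section has the equivalent for placebo. No other trigger is written in either section.

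**Recurrence.** Study Design says: "In the case of AA recurrence after ablation, AAD initiation or change will be left to the discretion of the treating physician". It also says: "Physicians will be advised to avoid adjustments in drug therapy unless absolutely necessary", and gives severe symptoms, newly diagnosed heart failure and NYHA Class IV as examples in an open-ended list. Cardioversion appears among the secondary endpoints, with no rule on when it is done.

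**Boxed warning.** The dronedarone part of the adverse-event section says that the patient groups behind the warning are excluded at entry. It repeats that the drug is contraindicated where AF cannot be cardioverted, but attaches no on-treatment action.

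**Appendix C, section 5.2**, under a heading on permanent AF: "Cardiovert patients who are in atrial fibrillation (if clinically indicated) or discontinue MULTAQ", and "Patients treated with dronedarone should undergo monitoring of cardiac rhythm no less often than every 3 months".

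**Rhythm monitoring.** The BodyGuardian section plans 30-day recordings from discharge and at 3, 6, 9 and 12 months. Study Schedule puts ±30 days on each visit after ablation. The same device section says: "Patients will be informed that ECG rhythm strips and associated results are not read in real-time". Recording between these periods is voluntary.

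**The concern.** Entry criteria cannot cover a patient who enters eligible and then reaches sustained AF on treatment. For that patient, if symptoms are mild and no new AAD is started, the body is silent about trial product and its general advice leans against changing drugs. Appendix C, which belongs to the same protocol, addresses patients in AF directly and gives the doubled cardiovascular risk in permanent AF as background.

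Two things are at stake. The first is patient safety, judged by the protocol's own product insert. The second is consistency: without a stated provision, sites may reasonably differ in how long product continues after recurrence. Exposure after recurrence bears on the fibrosis co-primary endpoint and on the safety comparison. Site investigators also know the assignment, so practice could differ by arm.

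Detection matters for the same reason. If the scheduled recordings can lie further apart than the interval in Appendix C, a schedule followed exactly as written can miss that interval.

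**Working it through.** **1. The texts side by side**

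| Question | Body | Appendix C 5.2 |
|---|---|---|
| New AAD started | Trial product stops | Not addressed |
| AF recurs or persists, no new AAD | No trial-product provision; AAD initiation or change at physician discretion; advice to avoid adjustments | Cardiovert (if clinically indicated) or discontinue |
| Rhythm monitoring | 30-day recordings at nominal 3-month steps, ±30 days | At least every 3 months |

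The arms also read differently. The Control Group section has a sentence on recurrence; the Treatment Group section has none and depends on Study Design.

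**2. Inputs for the gaps**

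- Start windows (Study Schedule): discharge taken as Day 0; then Days 60–120, 150–210, 240–300 and 335–395.
- Wear: 30 days per recording (BodyGuardian section).
- Three months: 365.25 / 4 = 91.3 days.
- Assumptions: the device goes on at the visit day and is worn for the full 30 days. The Schedule of Events footnote requires only that events fall within their timepoint.

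**3. Formulas**

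- Nominal gap = next nominal day − (previous nominal day + 30).
- Longest gap = latest next start − (earliest previous start + 30).

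| Interval | Nominal gap | Longest gap |
|---|---|---|
| Discharge to 3 months | 90 − 30 = 60 | 120 − 30 = 90 |
| 3 to 6 months | 180 − 120 = 60 | 210 − 90 = 120 |
| 6 to 9 months | 270 − 210 = 60 | 300 − 180 = 120 |
| 9 to 12 months | 365 − 300 = 65 | 395 − 270 = 125 |

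**4. How much is on treatment**

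Both 120-day gaps (Days 90–210 and 180–300) lie wholly inside the 12 months of dosing. The 125-day gap runs from Day 270 to Day 395. If dosing ends at Day 365, 365 − 270 = 95 days are on drug and 30 are not.

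**5. Can they coincide?**

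Not all of them. The 3-to-6 maximum needs the 6-month recording to start at Day 210, and the 6-to-9 maximum needs it at Day 150. The 6-to-9 maximum needs the 9-month start at Day 300, and the 9-to-12 maximum needs it at Day 240.

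**6. Other scheduled checks**

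The Schedule of Events lists an ECG at screening only. The 30-day device is therefore the only scheduled on-treatment rhythm check, and the 6- and 9-month contacts may be phone calls. Arrhythmias are exempt from AE reporting because recordings are reviewed centrally. No section says when an AF finding from that review must reach the site.

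**The case against.** The strongest reply is that silence is not a rule. A reader might infer that the body keeps every patient with recurrent AF on trial drug until a new AAD is started. The documents do not support that. The new-AAD trigger is not stated to be the only one. On recurrence, "AAD initiation or change will be left to the discretion of the treating physician", and stopping trial dronedarone can be read as such a change. Investigators are unblinded for safety reasons, and cardioversions are counted as an endpoint. Appendix C is itself part of the protocol, is qualified by clinical indication and sits under a permanent-AF heading. All of this stands: there is no explicit contrary rule, and a site can follow Appendix C without breaching the body.

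On detection, the device section tells patients with AF-positive readings or AF symptoms to seek care at once. The vendor may alert sites to critical rhythms. Outcomes are reviewed at the 6- and 9-month contacts, and standard-of-care or personal ECGs may fill gaps. These lessen the concern, but none is a scheduled rhythm check with a reporting time, and voluntary recording cannot guarantee an interval.

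The nominal timetable agrees with Appendix C, and the long gaps need one recording at its earliest day and the next at its latest. That also stands. Setting start-to-start intervals (up to 155 days) against 91 would overstate the matter, because each includes 30 days of recording.

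A reader might also size the hazard by applying the planned recurrence rate to the dronedarone arm. That rate counts any atrial arrhythmia over 30 seconds, blanking period included. It does not measure sustained or permanent AF.

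**Conclusion.** The point holds as an unreconciled omission, together with visit windows wider than the protocol's own monitoring interval. It does not hold as a direct contradiction about keeping patients on drug.

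Three of the four intervals can exceed about 91 days between scheduled recordings. Two do so by up to 120 − 91 = 29 days entirely on treatment. For the third, the on-treatment part is about 95 days, only slightly over. The discharge-to-3-month interval stays within 3 months at 90 days. This rests on full 30-day wear, device start on the visit day, dosing that ends near Day 365, and counting from the end of one recording to the start of the next, which is the reading kinder to the plan.

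The number of patients who would reach sustained AF on trial product, and any effect on the fibrosis result, cannot be sized from the documents. Site-to-site variation is a plausible consequence, not a demonstrated one. The point is still more than missing detail, because windows followed as written can breach the interval in Appendix C.

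**What to change.** - Reconcile Study Design, both treatment-group sections, the device section, the visit windows and the dronedarone safety text with Appendix C 5.2. State in the body, in the same words for both arms, what happens to trial product when AF recurs and persists without a new AAD.
- State when AF findings from the recordings reach the site.
- Time each device dispatch from the previous recording, so that the schedule and the Appendix C interval agree.

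Which clinical rule applies is for the sponsor, DSMB and investigators; none is proposed here.

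The cost is amendment wording and a tighter device-shipment window, with no new procedure. There may be some earlier product stops. The treatment-group sections already continue follow-up after discontinuation, and the primary analysis is already by intention to treat.

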### *Control Group (Placebo)*

Patients randomized to the control group will receive an initial placebo dose after cardiac ablation. In the case of AA recurrence, initiation of AADs will be left at the discretion of the treating physician, with recommendations to limit the use of AADs to essential cases only and to avoid prescribing amiodarone or dronedarone. In the case of a new AAD initiation, placebo treatment will be discontinued. The patient will continue to be monitored for fibrosis progression and AA recurrence/AF burden post-ablation. The

---

 Please see **Appendix A: Placebo Composition** for more information.

Page 16 of 49

evaluation of co-primary endpoints as well as all secondary endpoints will continue to be recorded throughout the duration of the trial.

## **Randomization and Blinding**

---

### *Randomization*

Patients who meet the eligibility criteria will be randomly assigned in a 1:1 ratio (i.e. 50/50 chance of being assigned to either study arm). An Interactive Web Response System (IWRS) randomization software program will be used to assign each study participant to a study arm. Before randomization occurs, each study participant will be stratified by age (i.e. <65 years old and  $\geq$ 65 years old) and AF type (i.e. persistent and paroxysmal). Once randomization occurs, each study participant will also be assigned a participant ID number.

Randomization will occur after cardiac ablation for two major reasons. First, we want to make sure that each enrolled participant has recovered well from the procedure prior to randomization. Secondly, site investigators may desire to perform more lesions during ablation if they are aware of how the study participant was assigned (e.g. unconscious bias). Therefore, to minimize bias and to maximize balance across groups, study participants will be randomized after cardiac ablation.

### *Blinding*

This is a single blinded clinical trial. Therefore, study participants will be unaware as to whether they are receiving drug or placebo. Site investigators cannot be blinded to the treatment administered since these site investigators may also be medically treating the study participant at the same time. Site investigators will need to be fully aware of the medications and associated dosages administered to their study participants to maximize study participant safety. To mitigate bias, independent ECG rhythm readers and CMR scan readers will not have access to the patient's treatment arm. In addition, all investigators, study monitors, medical monitors, data analysts, and the study team may have access to information related to the treatment arms when required.

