#### *Dronedarone (Multaq®) and Matching Placebo Dose and Dosing Regimen*

Dronedarone or a matched dose of placebo will be administered orally twice a day for 12 months. The placebo used in this trial is a physical match to the drug product. The study participant will be required to document medication regimen adherence on paper or on an electronic drug diary.

The trial drug should be taken after a meal. It should also be taken with a large glass of water (~250 mL) and consumed over as short a time as possible. Study participants should be instructed to swallow the capsules whole and not chew them. Study participants who are randomly assigned to the treatment group will take two 400 mg dronedarone (Multaq®) tablets each day. Those assigned to the control group will take two placebo tablets each day. Please refer to the “**Dose Administration by Group Assignment**” table below for more information.

If the study participant forgets to take the scheduled dose, s/he should not take the dose more than 4 hours after the usual time and should continue treatment the next day. Any missed doses should be skipped altogether and should not be replaced or made up at the next scheduled dosing.

Dose Administration by Group Assignment		
Assigned Group:	Number of Study Participants:	Dose:
Treatment Group	n=165	400 mg dronedarone (Multaq®), taken orally twice a day for 1 year
Control Group	n=165	400 mg of placebo taken orally twice a day for 1 year

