### **Concomitant Medications**

Page 19 of 49

Version 4.0:  
Revision Date: April 27th, 2022

Copyright© April 2022 Tulane University School of Medicine, Academic Research Organization on behalf of the Principal Investigator.  
All rights reserved.

TULANE UNIVERSITY  
Academic Research Organization

Concomitant use of the following is prohibited in all patients, regardless of treatment arm and needs to be discontinued at a minimum of 24 hours prior to receiving the first dose of trial treatment:

Use of strong CYP 3A inhibitors, such as ketoconazole, itraconazole, voriconazole, cyclosporine, telithromycin, clarithromycin, nefazodone, ritonavir, or drugs or herbal products that prolong the QT interval and might increase the risk of Torsade de Pointes, such as phenothiazine antipsychotics (e.g. prochlorperazine, chlorpromazine, fluphenazine, trifluoperazine, and thioridazine) tricyclic antidepressants (e.g. clomipramine, amitriptyline, nortriptyline, desipramine, imipramine, and doxepin) certain oral macrolide antibiotics (e.g. erythromycin, roxithromycin, azithromycin, and clarithromycin), and Class I (e.g. quinidine, procainamide, disopyramide, mexiletine, lidocaine, and tocainide) and III antiarrhythmics (e.g. sotalol, amiodarone, and dofetilide).

Medication history and current medication use will be assessed at all study related time points. Please refer to the “**Study Schedule**” and “**Schedule of Events**” sections for outlines of appropriate study procedures for each specific study timepoint.

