### *Stratification, Randomization and Blinding*

After cardiac ablation, trial staff will stratify each participant by age (< or  $\geq$  65 years old) and type of AF (persistent or paroxysmal). After stratification, study participants will be randomized using a web-based randomization service. Other confounding variables will be adjusted for primary outcome's analysis, including UTAH fibrosis staging. As this is a single-blind trial, only patients will be blinded to the assigned treatment arm.

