#### *Database Lock*

Once the last patient has had their follow-up visit, the database cannot be locked until all data queries have been resolved. Quantitative data will be examined statistically, prior to locking the database. When all such verifications have been completed, the database will become locked, prior to any final data analyses for the EDORA trial.

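### Data analysts and the central study team may see treatment arms for no stated reason, while covariates, model choice and the per-protocol set are still to be settled from the data

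*Combined protocol and SAP*

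**What the plan says.** All references are to the combined protocol and SAP.

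- **Who is unblinded, and why.** The Blinding section states: "Site investigators cannot be blinded to the treatment administered since these site investigators may also be medically treating the study participant at the same time". It adds that these investigators need to know the medication for the participant's safety. It then widens access: "all investigators, study monitors, medical monitors, data analysts, and the study team may have access to information related to the treatment arms when required". The condition at the end is not defined, and no reason is given for anyone other than site investigators.
- **Who is masked.** The same section says that "independent ECG rhythm readers and CMR scan readers will not have access to the patient's treatment arm". The section on the BodyGuardian device describes ECG core-laboratory reviewers who do not know the arm, and the section on the three-month CMR has two blinded experts check the lesion regions. Yet Stratification, Randomization and Blinding says that "only patients will be blinded to the assigned treatment arm".
- **Before lock.** Database Lock says: "Quantitative data will be examined statistically, prior to locking the database". It sets no masking condition. Final analyses follow the lock.
- **Choices left to the data.** Section B (General Considerations) adds to the regression models any baseline factor found imbalanced between the arms. Section C adds potential confounders that it does not list, although Utah stage is named elsewhere as an adjustment factor. It selects a linear mixed model or GEE after looking at the outcome distribution, and chooses missing-data factors after examining what predicts missingness. It describes the per-protocol set only as patients who received assigned treatment per the dosing protocol.

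**The concern.** Masking of the people who clean and analyse the data matters most when the analysis is not fully specified. Here several decisions that can move the treatment estimate are open at the time the data are seen. If the people making them can also see the arms, a choice may be influenced by its effect on the result, knowingly or not, and nothing on record could show otherwise. The 5% level assumes that the test was chosen independently of the treatment comparison.

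The access is also unnecessary on the plan's own reasoning. The stated reason is bedside safety. A data analyst or a central data manager does not treat the participant.

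A smaller matter is that the blinding statements disagree. One section says only patients are masked, while three others describe masked readers. Reader masking is the main protection for both co-primary endpoints, so the text should be unambiguous about it.

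**Working it through.** **1. Does the stated reason cover the access granted?**

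| Group given access | Covered by the treating-physician reason? |
|---|---|
| Site investigators | Yes, as stated |
| Medical monitors | Not stated; they assess incoming SAEs |
| Study monitors | Not stated; they work with source documents at unmasked sites |
| Data analysts | No |
| Study team, including central data cleaning | No, where they have no treating role |

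**2. Which decisions are open while access is possible?**

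- Data verification and queries: before lock, with no masking condition.
- Per-protocol membership: loosely defined, no date for fixing it. It affects a robustness analysis; the primary analysis is ITT.
- Covariates: selected through between-arm baseline tests, which need the arm.
- Mixed model or GEE, and missing-data factors: selected after the data are examined.

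The last two may fall after lock, so masking that ended at lock would not reach them.

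**3. How much could arm-aware covariate choice matter?** The documents give no figure, so this is an illustration. Assumed: no true effect; a linear model; n = 330 × 0.80 = 264; four baseline covariates, each explaining 3% or 5% of the variance; the analyst reports the most favourable of the 2^4 = 16 possible sets. By simulation, the one-sided error is 4.8% (3% each) and 4.5% (5% each), against a nominal 2.5%. Repeat runs gave 4.0% to 5.4%. This is a deliberate worst case for one test with these inputs.

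**4. The limitation on physician-decided events.** The Blinding section contains no figure, so the plan's AA calculation is reproduced first.

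- Events: 165 × (0.50 + 0.335) = 137.8, i.e. 138.
- HR = ln(0.665)/ln(0.50) = 0.589.
- Freedman power: Φ(√138 × (1 − 0.589)/(1 + 0.589) − 1.96) = Φ(1.08) = 86%. The stated figure reproduces.

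The AA endpoint counts a new antiarrhythmic started for recurrence without a positive ECG (Primary Endpoints, item 1b) and a repeat ablation without ECG recurrence (Definition of Trial Outcome using ECG Device). Masked readers have no tracing to read for these. Suppose there is no true effect, recurrence is 50% in each arm, and *d* net percentage points of such events are added to control only:

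- E = 165 × (0.50 + 0.50 + d); HR = ln(0.50)/ln(0.50 − d)
- P(significant in favour of drug) = Φ(√(E/4) × |ln HR| − 1.96)
- For d = 0.05: E = 173.25, HR = 0.868, giving Φ(0.93 − 1.96) = 15.2%.

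| Net excess in control | AA test alone, one-sided |
|---|---|
| 0 | 2.5% |
| 2 points | 5.6% |
| 3 points | 8.0% |
| 5 points | 15.2% |

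The unit matters. If an extra event is given to 5% or 10% of control patients, many of them recur anyway, and the net excess is only about 2.3 or 4.5 points. Simulation with 20% loss then gives about 6% and 15%.

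**The case against.** The strongest reply has four parts.

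**Access is permissive, and the pre-lock examination reads as verification.** This stands in part. The Database Lock section goes on to call these steps verifications, and nothing says they are done by arm. A reader might infer that the plan has analysts review unblinded results before lock; the documents do not say that. They only fail to prevent it.

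**Covariate picking comes from under-specification, and masking until lock would not cure it.** This is right, and it shapes the fix: masking has to last until the choices are written down, not merely until lock.

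**Monitors cannot be masked while sites are not.** This stands. Accountability records separate drug from placebo, and monitors have source-document access. Changing database permissions would not mask them, so the fix does not include them.

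**Single-blinding is a declared choice.** A reader might infer that site investigators should be masked too, since "The placebo used in this trial is a physical match to the drug product", an IWRS is in place, and several drugs are "prohibited in all patients, regardless of treatment arm". The protocol itself accepts that knowing the arm can change behaviour before randomisation, where "site investigators may desire to perform more lesions during ablation if they are aware of how the study participant was assigned". The documents do not carry the inference that far. They give a safety reason for unblinding sites. The rules are not fully arm-neutral, because advice to avoid amiodarone or dronedarone is written for the control group only. The kit-label appendix carries a drug-name variable. Site unblinding is therefore a trade-off the sponsor made openly.

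**Conclusion.** The concern holds for data analysts and central data-cleaning staff. They may be given the arms for a reason that does not apply to them, while analysis choices remain open. This is a weakness in bias control; no sample size, event count, alpha or nominal power changes.

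Its size cannot be derived from the documents. The rise from 2.5% to about 4.0% to 5.4% assumes four covariates, a linear model and deliberate selection. The AA figures assume both the size and the direction of physician bias. The direction is not certain either, because the advice to limit antiarrhythmics in controls could push the other way.

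A reader might take any of these rates as the trial's false-positive rate. They are not: success requires both co-primary endpoints. The error of one test passes nearly in full to the trial conclusion only if the other endpoint is very likely to succeed.

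As a limitation only, AA events counted without a tracing are decided by physicians who know the arm, and the masked readers do not protect them. The masked readers do protect ECG-documented recurrence and the fibrosis readings.

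**What to change.** 1. In the Blinding section, remove data analysts and central data-cleaning staff from those with arm access. For the roles that remain, define when access is needed and log each use.
2. Keep the removed staff masked until two conditions are met: the database is locked, and the covariates, the mixed-model-or-GEE decision, the missing-data factors and the per-protocol set are fixed in a dated document prepared on masked data. The covariate rule in section B relies on between-arm tests and cannot be run masked, so it should give way to a named list of baseline factors.
3. Have any by-arm DSMB tables produced by a person who takes no part in cleaning or the final analysis.
4. Reconcile the statement that only patients are masked with the sections that describe masked ECG and CMR readers.
5. State as a limitation that AA events counted without a tracing are decided by physicians who know the arm.

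The cost is protocol wording, database role permissions and a separation of roles at the coordinating centre. Sites, treatment and follow-up are unaffected.
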